3.0 Inclusion and Exclusion Criteria*

- 3.1 Individual eligibility will be determined through the Physical Activity Readiness Questionnaire Plus (PAR-Q+), which is a self-reported health questionnaire. During a presentation of inclusion/exclusion criteria, informed consent will be obtained as well. A preliminary FDST will be performed following informed consent to determine if the potential participant is eligible to participate in the study and for group stratification purposes.
- 3.2 Inclusion: Participants must be between the ages of 18 and older, if they were healthy via the PAR-Q+, and scored a 2 or higher on the FSDT.

Exclusion: Participants have any current knee/hip pain, past knee/hip pathology in the past 3 months on their dominant leg or that the participant believes would impact their ability to participate in the study, or any past LE surgery in their dominant leg that the participant believes would impact their ability to participate in the study, a concussion in the past 3 months, or if they have any vestibular pathology.

3.3 Inclusion and exclusion of special populations

- Adults unable to consent- Excluded
- Individuals who are not yet adults (infants, children, teenagers)-
- Pregnant women- Excluded
- Prisoners- Excluded
- Non-English-Speaking Subjects- Excluded
- Students/Employees- Included

4.0 Study-Wide Number of Subjects*

4.1 This research study is not a multicenter study. The total number of subjects to be accrued from the LSUHS main campus is 38 participants.

4.2 N/A

5.0 Study-Wide Recruitment Methods

5.1 Potential subjects will be recruited via word of mouth from people who are local to Shreveport, LA and local clinical/academic settings during the spring of 2026.

5.2 During a mandatory meeting prior to the start of the study, participants will be screened. Participants will fill out a self-reported health questionnaire to determine if they have any underlying health conditions that would exclude them from participation in the study. Once informed consent has been obtained, participants will also be asked to perform a preliminary FSDT to determine if they have a score of poor (4+) or moderate (2-3) that would include them in the study.

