9.0 Procedures Involved*

- 9.1 This study is a randomized control trial with stratification. Preliminary data from a preliminary FSDT will be used for exclusion, stratification, and randomization so that we can avoid any bias in results. The FSDT is scored on a 0–6-point scale with 0-1 categorically defined as good, 2-3 as moderate, and 4+ as poor. A participant will be excluded from the study if their score is defined as good or a 0-1 score. Then, stratification will be based upon the participant's categorical FSDT score of either moderate or poor to ensure equal representation of the category in each group. Participants will be randomly assigned to either the control group (hip activation HEP) or the experimental group (Hip activation plus movement retraining HEP). Individuals will receive their HEP protocol in an opaque envelope to ensure allocation concealment. The dependent variables are the FSDT score (statistical and clinical significance) and Gmed and Gmax sEMG activation (peak and mean).
- 9.2 Research procedures being performed and procedures being to monitor subjects for safety or minimize risks

Recruitment and Informed Consent Procedures

- Potential subjects will be recruited via word of mouth from people who are local to Shreveport, LA and local clinical/academic settings. Once they are recruited, meeting will be held for all potential participants to obtain informed consent. Then, the participant will complete a self-reported health questionnaire and a preliminary FSDT. If a potential participant cannot be

present at this meeting, a meeting will be scheduled with the investigators to obtain these measures.

- To ensure confidentiality, participants will be given a random identification number after their informed consent is obtained. Participant scores on the initial FSDT screening will be recorded by ID. Randomized stratification will take place following enrollment of all participants to ensure an equal distribution of FSDT scores between the control and experimental groups.
- Following enrollment, participants will sign up with their participant number for preliminary data collection in the motion analysis lab in room 2-217 in the SHPS at LSUHS. The participants will be instructed to wear shorts and advised to not wear leggings, tights, or pants or any lotions, both of which could impact EMG placement and data collection.

Anthropometric data collection procedures

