- Age, sex, height, weight, BMI, and dominant lower extremity (LE) will be recorded in the rehabilitation faculty clinic by GD and DB during the first visit. The determinacy of the dominant leg is based on the leg chosen to kick a ball at a target.¹⁵

MVIC testing procedure:

- Participants will then take the elevator to the second floor and report to room 2-217 for sEMG and FSDT. Electrodes for sEMG will be placed on the gluteus maximus and gluteus medius muscles of the dominant leg via Seniam guidelines, and skin preparation following recommendations from The ABC's of EMG.¹⁶ The electrodes that will be used are self-adhesive Ag/AgCl Dual Electrodes by Noraxon. The placement of sEMG electrodes will be completed by GD for the female participants and DB for the male participants. Maximum Isometric Voluntary Contraction (MVIC) for the GMax and GMed muscle will be performed and recorded by GD and DB. SEMG data collection will be obtained for MVIC and during performance of the FSDT.
- The procedure for collection of the maximum volitional isometric contraction (MVIC) of the GMed will follow the protocol used in a study by Harput et al.¹⁷ The participant will lay on their side with their top leg extended at the knee and abducted and extended at the hip. The MVIC position of the GMax will follow the protocol used in a study by Selkowitz et al, with the knee flexed to 90 degrees in prone.^{18,19}

FSDT procedures

- Participants will be instructed on the procedure for the FSDT by MM. The FSDT consists of five consecutive repetitions of a forward step-down from a 20cm step, with one score given for the whole set of five repetitions.^{20,21} The participant will be allowed to take two practice repetitions before beginning the test. sEMG data and FSDT will be collected before and after the 8 week HEP.

HEP and Compliance Chart Education Procedures

- After the initial FSDT and randomization has been completed, the participant will be educated on the gluteal muscle activation exercises HEP by (GD or DB or MM) (control group) or movement retraining program and gluteal muscle activation exercise HEP by (GD or DB or MM) (experimental group). Participants will be educated the compliance chart by investigator (GD or DB or MM). Compliance chart data will be collected and analyzed during the third/final visits.

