- All participants will receive the HEP for hip muscle activation training. The HEP for hip musculature activation consists of five isolated hip activation exercises including side-lying clams, side-lying clams with trunk activation via side-plank, side-lying hip abduction, side-lying hip abduction with trunk activation via side-plank, and fire hydrants all of which improve hip gluteal recruitment. See HEP for appropriate exercise positioning, dosage, frequency, and advised progressions.
- Only participants in the experimental group will receive the movement retraining program HEP. The HEP will be a combination of single leg RDL, single leg squat, and standing split squat that have been used in previous research and are proved to get significant Gmed activation.^{11,12,13} They will also participate in the gluteal activation HEP program that have been proved to increase hip musculature recruitment.
- A compliance chart will be given to the participants to track each time they perform the HEP. The participants in the control group and experimental group will take home their HEP, a compliance chart, then a yellow and red TheraBand. The participants will complete their HEP two days/week for eight weeks, with at least two rest days between sessions for muscle soreness prevention and document the completion of the session on the compliance chart.
- After the 4th week, both groups are to return to the clinic and asked to briefly perform exercises from their HEP so that their form can be reassessed with any modifications if needed along with any questions that they may have. Each participant following the 8-week period will be scheduled to return to the clinic to turn in their compliance form and perform follow-ups sEMG, weight, and FSDT using the same procedures as before.

Randomization of Group Allocation: Following the baseline EMG and FSDT measures, participants will be handed an opaque envelope containing their group allocation. Participants in the control group are indicated by a “0”, and intervention group by a “1”. A sequence of 1’s and 0’s will be generated by random generation in Excel, and the assignment will be made by sequential enrollment. To avoid unequal distribution of movement quality between groups, initial stratification in to “fair” and “poor” FSDT performance will be established after informed consent. Each strata will have an equal distribution of control and intervention envelopes.

9.3

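### Eligibility and strata come from a screening FSDT, but the analysed baseline appears to be a later lab FSDT; no stance limb is named and the stratum is never updated, so balance on the analysed category is not secured

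*Combined protocol and SAP*

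**What the plan says.** **Screening test.** Section 5.2 places it at a meeting before the study starts: "participants will also be asked to perform a preliminary FSDT to determine if they have a score of poor (4+) or moderate (2-3". Section 3.1 states: "A preliminary FDST will be performed following informed consent to determine if the potential participant is eligible to participate in the study". Section 3.2 requires a score of 2 or higher. Section 9.1 gives the same test three uses: "Preliminary data from a preliminary FSDT will be used for exclusion, stratification, and randomization". The scale is "scored on a 0–6-point scale with 0-1 categorically defined as good, 2-3 as moderate, and 4+ as poor". Section 9.2 (Randomization of Group Allocation) fixes the stratum early: "initial stratification in to “fair” and “poor” FSDT performance will be established after informed consent". Section 9.1 gives the aim as having each category equally represented in the two arms.

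**Lab test.** After enrolment, participants book a session in the motion analysis lab (section 9.2). At this first visit, "dominant lower extremity (LE) will be recorded in the rehabilitation faculty clinic", using a ball-kick test. Electrodes then go on the dominant leg, and the sEMG and FSDT measures follow. The table in section 9.3 lists three FSDTs and two sEMG sessions. Section 11.1 analyses one pre and one post FSDT in a 2x2 repeated measures ANOVA.

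**Allocation.** Section 9.2 states: "Following the baseline EMG and FSDT measures, participants will be handed an opaque envelope containing their group allocation".

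**Not stated.** No section says which leg performs the FSDT, which FSDT is the pre value, or what happens if the lab score falls in a different category from the screening score.

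**The concern.** The design stratifies on one measurement and appears to analyse another. The strata exist so that the arms start with the same mix of moderate and poor movers. SA2 analyses that category and SA1 the score behind it. If many participants change category between the two tests, balancing on the first gives only partial balance on the second. With about 17 per arm, chance imbalance is then not small.

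The limb adds to this. The exclusion criteria in section 3.2 already refer to the dominant leg, yet the only step that determines dominance comes at a later visit. The lab FSDT is recorded with electrodes on the dominant leg, while the screening FSDT has no stated limb.

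A participant who scores 0-1 at the lab test is already in the best category. That person cannot improve on SA2 and has at most one point to gain on SA1.

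**Working it through.** **1. Which FSDT is analysed.** Section 9.3 lists three FSDTs and two sEMG sessions. Section 9.2 pairs sEMG with the FSDT before and after the eight-week programme. The two paired FSDTs are therefore lab baseline and post-test, and the unpaired one is screening. This is an inference; section 11.1 does not say it.

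**2. Visit order.** Section 9.2 collects the compliance chart at the third and final visit, and the week-4 check lies between. The first visit, where dominance is recorded, is thus the lab baseline visit, after the screening meeting.

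**3. The plan's sample size.** Section 11.2 starts from 26, with 20% attrition and 10% screening failures: 26 / (1 - 0.20 - 0.10) = 37.1, rounded up to 38. This reproduces, and nothing below changes it. Taking 10% off for screening failure leaves 38 x 0.90 = 34.2, about 34 randomised.

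**4. How many change category.** The documents give no SD or reliability, so these are assumed: SD 1.1, reliability 0.7 to 0.9, the same limb throughout, a normal score rounded to whole points on 0-6. The mean is set so that 10% score 0-1 at screening: 1.5 + 1.28 x 1.1 = 2.91. Simulated, keeping those with a screening score of 2 or more:

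| Reliability | Lab score 0-1 | Lab category differs from stratum (includes the 0-1 group) |
|---|---|---|
| 0.7 | 5.9% | 30% |
| 0.8 | 4.9% | 24% |
| 0.9 | 3.5% | 17% |

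Of 34, that is 34 x 0.035 = 1.2 to 34 x 0.059 = 2.0 people at 0-1, and 34 x 0.17 = 5.8 to 34 x 0.30 = 10.2 in a different category.

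Other assumptions give a wider range. With mean 3.0 or 3.5, SD 1.3 (12% or 6% screening failure) and reliability 0.50 to 0.95, 1.6% to 9.2% score 0-1. A further 10.7% to 33.8% cross the cut between 3 and 4.

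**5. Effect on balance.** About 33% are poor at the lab test under the step 4 inputs. With 17 per arm and no stratification, the SD of the between-arm difference in that share is sqrt(0.33 x 0.67 x (1/17 + 1/17)) = 0.16. Simulated with 34 randomised:
- stratified on the screening score: about 0.12 to 0.14;
- stratified on the lab score: about 0.03 to 0.04, depending on how odd stratum sizes are split.

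The planned stratification therefore recovers only a small part of the balance available.

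**6. Does selection distort the pre-to-post change?** A third test was simulated with no treatment effect. The mean change from lab to post is 0.00 at every reliability, because selection used a separate, earlier test. If only those with a lab score of 2 or more were randomised, the change with no effect would be -0.02 to -0.06.

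**The case against.** The strongest reply is that the plan defines the strata by the preliminary FSDT. A stratifier measured with error before randomisation is still valid, and the ANOVA in section 11.1 does not use the stratum. That stands: the between-arm comparison remains unbiased, and the loss is one of balance.

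Three stronger readings are tempting, and the documents do not support them.

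- *Regression to the mean biases the result.* Step 6 shows no spurious change from lab to post. A fall measured from screening would contain selection, but section 11.1 appears to plan no such comparison.
- *Participants are screened on the wrong leg.* Section 9.2 says when dominance is recorded, not that it is unknown earlier. The dominant-leg exclusions in section 3.2 suggest that someone has it in mind at screening. The gap is an unstated limb, not a demonstrated mismatch, and no figure can be put on it.
- *Anyone scoring 0-1 in the lab should be excluded.* This would select on the analysed baseline and create the artefact in step 6. It would also cost participants: 38 x 0.90 x 0.80 = 27.4 expected completers becomes 27.4 x 0.94 = 25.7 to 27.4 x 0.97 = 26.5, against 26 required.

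Section 13.2 allows withdrawal of someone who no longer meets the criteria. It sets no check at the lab visit and, read literally, would also remove a participant who improves to good. It cannot serve as the missing link and should be reconciled with sections 3.2 and 9.2.

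**Conclusion.** The point holds as a matter of balance and clarity, not bias. The sequence is in the text; that the lab FSDT is the pre value is a sound inference that the plan should confirm. Under the step 4 assumptions, about 6 to 10 of 34 participants would have a lab category different from their stratum, and about 1 to 2 would start at 0-1. These counts rest on an SD and a reliability that the documents do not give. The case for change does not need the exact figures, because any imperfect reliability moves people across the cuts and the repair is cheap. Severity is minor to moderate.

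**What to change.** 1. Do the ball-kick check at the screening meeting, before the preliminary FSDT. State in section 9.2 that the dominant limb is the stance limb at screening, baseline and post-test.
2. Draw the envelope from the stratum given by the lab score, which is known before the envelope is handed over. Place a participant who scores 0-1 there in the moderate stratum. Score the lab FSDT on the spot.
3. Reconcile section 9.2 with itself. One paragraph randomises after all participants are enrolled and before lab sessions are booked; another assigns by sequential enrolment after the baseline measures. Use one name for the middle category, which appears as both moderate and fair.
4. State in section 11.1 that the lab score is the pre value for SA1 and SA2. Settle whether one rater scores (11.1) or three scores are averaged (11.4), since an average such as 3.33 has no category.
5. Keep eligibility on the screening score.

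**Cost.** A short check moves earlier and some wording changes; no test is added and N is unchanged. The one downside is that stratum sizes are known only as participants reach the lab. Envelopes should therefore be prepared in balanced blocks within each stratum, with enough spare to cover either split.

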5.3 N/A

6.0 Multi-Site Research

6.1 N/A

6.2 N/A

6.3 N/A

7.0 Study Timelines

7.1 The duration of the individual subject's participation in this study is currently 590 minutes or 9.8 hours during the study which will last for 8 weeks. Data collection consisting of anthropometrics, sEMG, FSDT, and HEP education will require ~45 minutes for measurements and recording of

data. Following completion of assigned HEP, FDST and sEMG will be measured and the data will be recorded. Both HEPs will take no more than 25 minutes a session to complete; hence, allocating 50 minutes in total each week since two sessions will be completed per week. A mid-participation session at 4 weeks is expected to take less than 15 minutes to ensure correct exercise completion, and the post-testing is expected to take 20 minutes.

- The duration anticipated to enroll all study subjects is estimated to be done over a month during January 2026.
- The estimated completion date of this study, including data analysis, is June 2026.

8.0 Study Endpoints

- 8.1 Both primary and secondary study endpoints will be the completion of data collection and intervention for all participants. This will be completed by May 2026. Data analysis will be completed by June of 2026.
- 8.2 This is a low-risk study. Participants who experience safety concerns during the testing process will be stopped. No safety risks from receiving the intervention or dropping out of the study are predicted.

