12.0 Provisions to Monitor the Data to Ensure the Safety of Subjects*

12.1 N/A

13.0 Withdrawal of Subjects

- 13.1 Non-study injuries that affect the ability to complete HEP or FSDT post-intervention will be withdrawn from the research without their consent.
- 13.2 If a participant no longer meets the inclusion or exclusion criteria or if the subject notifies the investigator that they no longer wish to continue participation in the study, the investigators will notify the participant that they have withdrawn from the study and will document the date and reason for withdrawal. The participant will return the compliance sheet to the investigators.

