13.3 N/A

14.0 Risks to Subjects

- 14.1 As with any exercise program, muscle soreness is a potential side effect. To reduce these potential side effects, participants will be asked to make sure that they put two days in between completing the HEP. Another risk with any exercise program is the potential risk of injury. To reduce these potential side effects participants will meet with investigators to be instructed on how to perform the exercises safely and will be cued during the HEP on proper form to complete the exercises .

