- Our study has less than minimal risk, thus no medical or psychological resources should be needed due to there being no anticipated consequences of human research.
- The PI will complete the DOA, including the assigning of roles and responsibilities, and educate each investigator at the time of signing.

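### Sections 8.2 and 20 predict no harm from the intervention while 14.1 lists soreness and injury, and the text plans no systematic recording of these in participants who continue, nor any summary by arm

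*Combined protocol and SAP*

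**What the plan says.** Two sections say that no harm is expected. Section 8.2 reads "No safety risks from receiving the intervention or dropping out of the study are predicted". Section 20 reads "no medical or psychological resources should be needed due to there being no anticipated consequences of human research", having just rated the study below minimal risk.

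Section 14.1 says otherwise: "As with any exercise program, muscle soreness is a potential side effect", and then "Another risk with any exercise program is the potential risk of injury". It goes on to describe steps meant to reduce both.

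On detection and recording:

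- The section 12.0 heading, "Provisions to Monitor the Data to Ensure the Safety of Subjects", is answered N/A.
- Section 8.2 provides that "Participants who experience safety concerns during the testing process will be stopped". This covers the testing visits.
- Section 9.2 brings both groups back after week 4 so that their form can be looked at and their questions answered. The home log is described there as a record of completed sessions.
- The data lists in 9.4 and 11.5 name anthropometrics, FSDT, video, sEMG and compliance. They name no pain, soreness, injury or adverse-event item. The analysis plan in 11.1 covers FSDT and sEMG only.
- Section 13.1 withdraws participants whose injuries arise outside the study. Section 13.2 applies "If a participant no longer meets the inclusion or exclusion criteria" or if the participant asks to leave, and requires the date and the cause to be written down.

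**The concern.** There are two linked problems. The first is one of consistency: a reader of 8.2 or section 20 is told to expect no harm, and a reader of 14.1 is told to expect possible soreness and injury.

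The second is that the plan does not set out to observe the risks it lists. Only the experimental arm adds single-leg deadlifts, single-leg squats and split squats to the shared gluteal program, so a difference in soreness or pain between arms is a natural question. A harm that nobody asks about cannot be recovered at analysis.

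The gap also touches the plan's own rules. Current knee or hip pain is an exclusion in 3.2, and 13.2 acts on loss of eligibility, yet no planned question would bring new pain to light.

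Interpretation is affected too. SA5 relates adherence to response. Soreness could lower both, and if it is not recorded it cannot be considered when reading that result or the reasons for drop-out.

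**Working it through.** **Step 1. Set the risk statements side by side.** 8.2: no risk from the intervention is predicted. Section 20: no consequences are anticipated. 14.1: soreness and injury are both possible. 8.2 does open by calling the study low-risk, which fits 14.1, but its last sentence does not.

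**Step 2. Ask where each type of event would be captured under the text as written.**

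| Event | Provision in the text |
|---|---|
| Safety concern during testing | Testing is stopped (8.2); no data item is named |
| Knee or hip pain that ends participation | Cause of withdrawal documented (13.2), linkable to arm by ID (11.3) |
| Injury from outside the study that prevents completion | Withdrawal (13.1) |
| Injury from the home program that ends participation | Not named in 13.1; could enter through 13.2 |
| Pain, soreness or injury in a participant who continues | None described |
| Summary of any of these by arm | None described |

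The week-4 visit might reveal a problem through observation or a participant's own question, but no question to the participant and no data item is stated.

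**Step 3. The plan's sample size, used as the base for exposure.** Section 11.2 gives d = 0.58, alpha 0.05 two-tailed, power 0.80 (printed as beta), N = 26, then 38 after 20% attrition and 10% screening failure. With f = d/2 = 0.29 and a noncentral F for the 2x2 interaction, N = 26 is reproduced (power 0.810) if the pre-post correlation is 0.5. The documents do not state that correlation; values of 0, 0.3 and 0.7 give N = 50, 36 and 18. The inflation is 26 / (1 - 0.30) = 37.1, rounded up to 38. The sample size does not bear on the safety gap; it only supplies the counts below.

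**Step 4. Planned home sessions.** Each participant has 2 per week x 8 weeks = 16, as in the table of events in 9.3.

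- 26 evaluable: 26 x 16 = 416
- 34 randomised: 38 x 0.90 = 34.2, taken as 34; 34 x 16 = 544
- 38 randomised: 38 x 16 = 608
- 34 randomised, 20% stopping halfway (an assumption): 34 x 0.8 x 16 + 34 x 0.2 x 8 = 489.6, about 490

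The documents do not settle whether 38 is counted before or after screening, so 416 to 608 is the fair range.

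**Step 5. What recording could show.** With zero events among n participants in an arm, the one-sided 95% upper bound for the proportion affected is 1 - 0.05^(1/n).

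- n = 17: 1 - 0.05^(1/17) = 16.2%
- n = 19: 1 - 0.05^(1/19) = 14.6%

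The chance of seeing at least one event with n = 17 is 1 - (1 - p)^17, which is 58% for a true proportion of 5% and 83% for 10% (illustrative values).

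**The case against.** The strongest reply is that this is a short, low-risk program in adults screened with the PAR-Q+, that safeguards are in place, and that 8.2 against 14.1 is a matter of one sentence. The safeguards are real. Testing is stopped for safety concerns, investigators watch each participant exercise after week 4, sessions are spaced to limit soreness, and causes of withdrawal are written down.

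A reader might therefore infer too much from the N/A in section 12.1. Three stronger readings are not supported:

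- *Nothing is monitored.* The provisions just listed contradict this.
- *An injury from the home program has no place to be recorded.* If it ends participation it can enter through 13.2 and be linked to arm.
- *The experimental arm does loaded exercise.* The text states no external load for the retraining exercises. The resistance bands belong to the hip activation exercises, and both arms take them home.

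Two further objections stand in part. The compliance chart, data collection form and detailed home program are separate documents, so a pain field on one of them cannot be excluded; the text describes none. And with about 17 per arm, recording would not settle whether one arm causes more injury unless the difference were very large. That limits what the data can prove, but it is no reason to leave the events unasked.

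**Conclusion.** The point holds in limited form. The statements in 8.2 and section 20 conflict with 14.1 and must be reconciled. Separately, the text plans no systematic recording of pain, soreness or injury in participants who continue, and no summary of harms by arm, over about 416 to 608 planned home sessions. The figure of 544 requires 34 randomised participants who each complete all 16 sessions.

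The conclusion rests on the protocol text alone; a field on an unseen form would narrow it. No planned efficacy test depends on it. Any harms data collected would be descriptive, since even zero events in an arm of 17 would leave a proportion of up to about 16% compatible with the data. It is a worthwhile, low-cost improvement and not a fatal flaw.

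**What to change.** 1. Add a column for pain, soreness or injury to the per-session compliance chart, if it does not already have one.
2. Ask one identical question on these events in both arms at the existing week-4 and week-8 visits, and add the item to the lists in 9.4 and 11.5.
3. Add to 11.1 one descriptive table by arm giving participants affected and number of events, without a significance test.
4. Reconcile 8.2 and section 20 with 14.1, and make clear in section 13 where an injury arising from the home program is documented.

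The cost is one chart column, one question at two visits already scheduled, one table and a few sentences. The downside is a minor burden on participants. No clinical rule on stopping or managing exercise is proposed.
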